The qualitative variables analysed were: gender, body mass index (BMI) by rank, sock type, dermal lesions (all lesions developed during the hike, both keratopathies with keratinisation disorder and dermatopathies without keratinisation disorder), muscle lesions (all lesions developed during the hike) and nail lesions (all nail lesions developed during the hike, both traumatic and non-traumatic onychopathies). The height and weight data obtained were used to calculate BMI by rank, interpreted according to the World Health Organization classification [41] (Table 2).

Table 2. Qualitative variables and categories. BMI= Body mass index.

Qualitative variable	Category	
Gender	Male Female	
BMI	Underweight (<18.5) Normal weight (18.5-24.99) Overweight (25.0-29.9) Obese ((>30)
Sock type	Technical (Tierra) Technical (Set) Non-technical (Cotton)	
Skin lesion	Blister Injury (Erosion & chafing) Reddened skin Urticaria Crevice H	Ieloma
Muscle lesion	Pain due inadequate warm Inflammation Muscle discomfort Sprain	
Nail lesion	Onychocryptosis Subungueal hematoma	

The quantitative variables analysed were: age, body mass index (BMI), temperature of each foot measured in two aspects (plantar and dorsal), and perimeter of each foot, measured in four areas (dorsal aspect of toes, instep, heel, tibia).

5. Measuring instruments

The height range and the pace hikers was controlled with a Garmin ETREX 20X GPS (Global Positioning System). Perimeter was measured with a flexible, non-elastic tape measure (Lawton 18-0160, precision 1 mm). Weight was measured using scales (Tanita UM-076, precision 0.1kg) and height was measured using the weight rod of different scales (SECA 704, precision 1 mm).

Temperatures were taken with an infrared thermometer (FTN Medisana, precision 0.18° C), calculating the mean of the three measurements. An intra rate of the measure was done to detect the error of the measure of the temperature, obtaining an error of 0.1452.

6. Statistical tests

The data were analysed using IBM SPSS Statistics for Windows, Version 22.0 (IBM, Armonk, New York). The statistical treatment consisted of data study and cleansing, descriptive variable analysis, normality test (Shapiro-Wilks test). The studies of normality were no significant (p-values between 0.000 y 0.044).

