Quantitative variables depending on whether the samples were paired or independent, Friedman's test for related samples and Kruskal-Wallis was performed for independent samples, both with Bonferroni correction for multiple testing was applied. For the qualitative variables the

chi-square or Fisher's exact test with a significance level of α = 0.05 was carried out. The variables analysed by logistic regression were quantified using the ODDS Ratio (OR). The effect size for the different variables was also calculated. First, for Kruskall-Wallis tests, the variation was between 0.443 y 0.888, and for Friedman tests, the variation was between 0.336 y 0.623. Therefore, in both cases the effect size could be considered median and high.

All p-values = 0.000 are less than 1 per 1000.

Results

After completing the first part of the hike, the most frequent dermal lesions among participants were blisters and erosions.

Table 3. Prevalence of skin, muscle and nail lesions during the 0-14.5 km of the hike by sex.

(0.14 = 1)				Fen	nale					Ma	ıle		
(0-14.5 km)		Tier	ra %	Se	et %	Cott	on %	Tier	ra %	Set	%	Cott	on %
Skin lesion	%Tt.	RF	LF	RF	LF	RF	LF	RF	LF	RF	LF	RF	LF
Blister	12.8	0.0	4.0	8.0	7.7	22.2	27.8	0.0	5.3	5.3	0.0	6.7	13.3
Erosion	2.8	0.0	0.0	0.0	0.0	11.1	5.6	0.0	0.0	0.0	0.0	6.7	0.0
(0.44.5.1)				Fer	male					Ma	ıle		
(0-14.5 km)		Tier	ra %	Se	et %	Cott	on %	Tier	ra %	Set	%	Cott	on %
Muscle lesion	%Tt.	RF	LF	RF	LF	RF	LF	RF	LF	RF	LF	RF	LF
Pain due inadequate warm	21.1	23.1	27.8	8.0	7.7	27.8	27.8	10.5	15.8	10.5	0.0	13.3	13.3
Inflammation	2.8	0.0	4.2	4.0	0.0	0.0	0.0	0.0	10.5	10.5	0.0	0.0	0.0
Muscle discomfort	1.8	0.0	0.0	0.0	0.00	0.0	0.0	5.3	5.3	0.0	0.0	0.0	0.0

Km=Kilometres, %=Percentage, Tt=Total, RF=Right foot, LF=Left foot.

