The study of the perimeter of hikers' feet analysed in total and by gender, in relation to distance and sock type, did not reveal significant results (data not shown).

Table 7. Probability of suffering skin and muscle lesions in relation to anthropometric variables and sock type throughout the hike.

1	PROBABILITY SKI	N LESIONS	PROBABILITY M	USCLE LESIONS		
Dist	ance:	Distance: 14.5-29.6 Km	Distance: 0-14.5 Km			
96% If	female	90% If male	100% I	f male		
100% If non-	technical sock	100% If non-technical sock	67% If non-te	chnical sock		
Direct relation	Inverse relation	Inverse relation	Direct relation	Inverse relation		
BMI	Age	Age	BMI	Age		

km=Kilometre, %= Percentages, BMI=Body mass index.

It was possible to study the relation between variables and predict the probability of lesions developing during the hike using logistic regression analysis (Table 7). Women have a higher probability than men of suffering skin lesions in hikes of up to 14.5 km. However, men have a higher probability than women of suffering skin lesions on hikes of 14.5 to 29.6 km and muscle lesions on hikes of up to 14.5 km.

The non-technical socks showed the highest probability of wearers suffering dermal and muscle lesions, both from 0-14.5 km and from 14.5 km to the end of the hike. The probability of dermal and muscle lesions developing in relation to the quantitative variables showed direct and inverse relations. From 0-14.5 km, the BMI and age of hikers are directly and inversely related, respectively, both in dermal and in muscle lesions. In the second part of the hike, age continued to show an inverse relation with skin lesions, but no relation with BMI was identified (Table 7).

Supplementary data

Protocol of Measures. Top shows the protocol of measure at the starting point (0 km). Middle part includes the protocol of the first part of the hike (0-14.5 km) and lower part of the table reflex the measurement protocol of the second part of the hike (14.5-29.6 km)

PPOTOCOI	OF MEASURES
STARTING POINT (0 Km)	OF MEASURES
Dorsal Number: Gender: Gender:	Foot size Weight Size
Body mass index (BMI):	The state of the s
	Previous Alterations on skin, muscles or
nails	
	rature LF
Plantar Plantar	
Dorsal Dorsal	
Perimeters RF: (Three different measures)	Perimeters LF: (Three different measures)
tibia	tibia
hell	hell
toes instep	toes instep
FIRST PART OF THE HIKE (0-14.5 Km)	Perimeters RF: (Three different measures)
	tibia
Temperature RF: (Three different measures)	
Plantar	

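### Previous skin, muscle and nail alterations are recorded at km 0 but appear in no reported analysis, so no sock effect is adjusted for them and three sparse foot-level results rest on an unstated rule for what counts as new

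*Combined protocol and SAP*

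**What the plan says.** The starting-point part of the Protocol of Measures (Supplementary data) includes a field for "Previous Alterations on skin, muscles or" nails. As the form reads in the text available, this is a single entry. The instruction to specify right or left foot appears only on the lesion lists for the two hike sections.

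Section 4 (Study variables) gives two lists. One begins "The qualitative variables analysed were: gender, body mass index (BMI) by rank, sock type, dermal lesions" and goes on to muscle and nail lesions. The other begins "The quantitative variables analysed were: age, body mass index (BMI), temperature of each foot measured in two aspects" and ends with foot perimeter. Previous alterations are in neither. The same section defines the outcome as "dermal lesions (all lesions developed during the hike", with matching definitions for muscle and nail lesions.

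Section 6 (Statistical tests) says of the model only that "The variables analysed by logistic regression were quantified using the ODDS Ratio (OR"), with no covariate list or selection rule. For qualitative variables, "chi-square or Fisher's exact test with a significance level of α = 0.05 was carried out". The Results use the model to "predict the probability of lesions developing during the hike using logistic regression analysis". Table 7 is titled "Probability of suffering skin and muscle lesions in relation to anthropometric variables and sock type throughout the hike", and the predictors it shows are sex, sock type, BMI and age. No result reports the km 0 item, and Table 1 gives no baseline characteristics by sock group.

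**The concern.** A foot that starts with damaged skin or a damaged nail may be more likely to have a lesion during the hike. The eligibility criteria in Section 1 exclude only health problems that would hinder or prevent taking part, so minor alterations can be present at the start. With 33 cotton hikers and 76 technical hikers, some imbalance in such a factor is expected by chance. It could be larger if hikers were not randomised to cotton, and Section 3 describes that step only loosely.

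There is a second, separate issue. The outcome is meant to be incident, but no step is described that compares the km 14.5 or km 29.6 examination with the km 0 record. Where a reported difference rests on three or four feet, that rule decides the result.

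**Working it through.** **Reproducing the reported contrasts.** Counts follow from the percentages and group sizes; tests are two-sided Fisher.
- 0-14.5 km: 5/76 = 6.6% vs 12/33 = 36.4%, difference 29.8 points, p = 0.0002 (stated 0.000), risk ratio 5.53.
- 14.5-29.6 km: 16/76 = 21.1% vs 17/31 = 54.8%, difference 33.8 points, p = 0.0011 (stated 0.001), risk ratio 2.60.

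The second-section percentages fit only 31 cotton hikers (16 women), whereas Section 3 says both dropouts wore technical socks. Those statements need reconciling. The counts below use the denominators that fit the tables.

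**Size of the missing adjustment.** The adjusted effect cannot be computed, because no count of previous alterations is given. The following is assumed.
- Chance SD of the difference in prevalence q between groups: sqrt(q(1-q)(1/76 + 1/33)). At q = 0.30 this is sqrt(0.21 x 0.04346) = 0.096. At q = 0.10 it is 0.063, and at q = 0.50 it is 0.104.
- If alterations raise lesion risk from 10% to 25% (15 points), one SD shifts the contrast by 0.096 x 15 = 1.4 points, with a range of 0.9 to 1.6 for q from 0.10 to 0.50.
- Harsher case: a chance imbalance of 1.96 SD against cotton, with a factor-lesion risk ratio R of 2 to 5. The bias factor is B = [1 + p_cotton(R-1)]/[1 + p_technical(R-1)]. At q = 0.20 and R = 5, p_cotton = 0.314 and p_technical = 0.151, so B = 2.256/1.604 = 1.41. Over q from 0.10 to 0.50, B runs from 1.12 to 1.41. The risk ratios would move from 5.53 to 3.9-5.0, and from 2.60 to 1.85-2.34.
- Simulation with hikers randomised (q 20-40%, factor odds ratio 2-4): type I error 0.054-0.060 unadjusted and 0.050-0.055 stratified, with power differing by at most about 2 points.

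**Reclassifying cotton hikers only.** Recounting lesions as old in cotton hikers, and none in technical hikers, the first section has p = 0.042 after five and 0.085 after six. The second has p = 0.033 after four and 0.088 after five.

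**Foot-level findings, 14.5-29.6 km.** In each, all e events fall in one sock group of n feet out of N. Pearson chi-square on 2 df is then X2 = N e (N-n)/[n(N-e)], and p = exp(-X2/2).

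| Finding | Counts | X2 | p (stated) | p with one lesion recounted as not new |
|---|---|---|---|---|
| Women, reddened skin (each foot) | cotton 3/16; others 0/13 and 0/25 | 54x3x38/(16x51) = 7.54 | 0.023 (0.023) | 54x2x38/(16x52) = 4.93, p = 0.085 |
| Men, RF erosion | cotton 3/15; others 0/19 and 0/19 | 53x3x38/(15x50) = 8.06 | 0.018 (0.018) | 53x2x38/(15x51) = 5.27, p = 0.072 |
| Men, LF blister | Set 4/19; others 0/19 and 0/15 | 53x4x34/(19x49) = 7.74 | 0.021 (0.021) | 53x3x34/(19x50) = 5.69, p = 0.058 |

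The last column keeps the foot in the denominator as lesion-free. If the foot is dropped instead, reddened skin gives 53x2x38/(15x51) = 5.27, p = 0.072, and erosion gives 52x2x38/(14x50) = 5.65, p = 0.059. Blister gives 52x3x34/(18x49) = 6.01, p = 0.049, so it stays just under 0.05. The counting rule therefore matters as well as the lesion.

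**The case against.** The strongest reply is that the outcome is already incident by definition, and that the form keeps the km 0 entry apart from the two lesion lists. On this view only a description is missing. Much of this stands.

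A reader might infer that heloma and onychocryptosis in Table 4 are old lesions re-recorded as new. The documents do not support that. The Results report no heloma and no nail disorder at km 14.5, where existing ones should have been visible. Each is one hiker (0.9%). The onychocryptosis was on a woman's Tierra foot, so carry-over there would count against a technical sock. Removing the one cotton heloma hiker's event leaves 16/31 vs 16/76, p = 0.003.

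A reader might also infer that any carry-over inflates the sock effect. Carry-over unrelated to sock dilutes it: an assumed 5% in both groups multiplies the difference by 0.95, from 29.8 to 28.3 points and from 33.8 to 32.1.

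Three further limits stand. The covariate list is inferred from Section 4 and Table 7, so an item tried and dropped cannot be ruled out. The hiker-level p-values come from chi-square or Fisher tests, which a model covariate would not change. Events are few: 17 hikers with skin lesions at 0-14.5 km is 17/4 = 4.3 per predictor shown, and 17/5 = 3.4 with a fifth.

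The reply does not supply a stated rule separating old from new lesions, a table of the item by sock group, or any analysis that uses it.

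**Conclusion.** The omission is real and its consequence is limited. No reported sock effect is adjusted for previous alterations, and the documents neither show that the groups were balanced on them nor say how they were separated from new lesions.

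It would be wrong to read this as undermining the main contrast. Under random assignment and the assumptions above, the expected shift is about 1.4 points per chance SD against differences of about 30 and 34 points. Losing significance would take six cotton hikers (first section) or five (second) reclassified, and none in technical socks. If hikers were not randomised to cotton, the chance-imbalance calculation no longer bounds the shift. That previous alterations predict lesions is plausible but not shown here.

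The practical weight falls on the three foot-level findings. One lesion counted differently takes each above 0.05 when the foot is kept as lesion-free. This shows fragility. It is not evidence that such a lesion existed.

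**What to change.** 1. Tabulate the km 0 item by sock group, by tissue where the record allows.
2. State the rule by which a lesion was counted as new.
3. Add km 0 alteration (yes/no, by tissue where possible) to the lesion logistic models, with a penalised or stratified fit because events are few. Report the adjusted sock odds ratio and interval beside the unadjusted contrast, and print the full covariate list.
4. Repeat the foot-level tests behind Tables 3 and 4 without any lesion recorded at km 0, matching by foot only where the km 0 entry identifies the foot. Say whether such feet stay in the denominator.

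No new data collection is needed if the field was completed. The cost is one more parameter in a sparse model, so slightly wider intervals. Matching by foot or tissue may be only partly possible, depending on what was written in the single km 0 entry.
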